4.3.2 EE-2

The Efficacy Evaluable Set will include all patients in the ITT-2 who had a complete disease response assessment. A complete disease response assessment was defined as at least 1 post-baseline peripheral blood count determined and 1 post-baseline bone marrow assessment

performed, with an Investigator response reported. A peripheral blood count was defined as an assessment of absolute neutrophil count (ANC), platelets and peripheral blasts. In addition, patients who discontinued due to progressive disease per the Study Discontinuation form without a complete disease response assessment will also be included in this Efficacy Evaluable Set. This will be the secondary set used for the analysis of the efficacy endpoint CRc rate.

4.4 PER PROTOCOL (PP)

This set will comprise patients who meet all eligibility criteria and receive randomized study treatment (i.e. study drug and AZA) without major deviations or violations. This set will be the secondary set analyzed for the efficacy endpoint OS.

Membership in above defined sets, especially in the PP set, will be determined prior to unblinding.

4.5 PHARMACOKINETICS (PK)

At least two sets will be defined for the PK analysis, the first set for analyzing the pracinostat data and the other set for analyzing the azacitidine data; this last set will be limited to the patients from selected sites included in the sub-study and who consented for the sampling for the PK of azacitidine. The possibility to participate into the PK AZA sub-study will be closed as soon as the requested number of patients is reached (set at present to at least 12 for each group); due to the blindness of the study, the unblinded statistician who takes care of the analysis for the IDMC will be responsible for checking the number of patients in each group. Detailed definitions of these sets and possible additional sets will be defined in the dedicated PK SAP.

5 CONSIDERATIONS FOR DATA ANALYSIS

5.1 PROGRAMMING ENVIRONMENT

All analyses will be conducted using SAS[®] version 9.4 or higher.

5.2 STRATA AND COVARIATES

Patients will be randomized 1:1 to one of the two treatment groups, stratified based on the following two factors:

- Cytogenetic risk category (intermediate vs. unfavorable-risk)
- ECOG (0/1 vs. 2) at screening

For the primary analysis the stratification used for the randomization will be used.

The results from the central assessment of the cytogenetic risk category and the ECOG grade assessed on day 1 of cycle 1 will be used as a sensitivity analysis (in case of discrepancies between the local and the central result of the baseline cytogenetic analysis leading to different cytogenetic risk categories compared to those used in the randomization process, the patient will be included in the risk category determined by the central assessment. In case the central result should not be available, the local result will be used instead).

The Kaplan-Meier estimates of the primary efficacy variable (Overall Survival) will be reported for the two treatment groups, overall and within the strata.

Also descriptive statistics (i.e. absolute and relative frequency for rates and Kaplan Meier estimates for the RFS and duration of responses) will be produced overall and within strata for the secondary and exploratory efficacy endpoints.

Other covariates with potential impact on the efficacy endpoints will be evaluated at the Blind Data Review Meeting (BDRM).

For the PK analysis demographic, physiopathological and therapeutic covariates will be used to determine the influence of these variables on PK parameters and their interindividual variability. Details will be described in the PK SAP.

Cases of randomized patients who performed a cycle with Azacitidine or Decitabine during the screening period will be evaluated at BDRM.

5.3 SUBGROUPS

The primary endpoint of OS and the secondary endpoints of CR, transfusion independence, CR_C, and CR_{M RD} will be also explored in each of the following subgroups: Intermediate Cyto risk (at randomization), unfavorable cyto risk (at randomization), ECOG 0-1 (at randomization), ECOG 2 (at randomization), ECOG 0-1 at Day 1 Cycle 1, ECOG 2 at Day 1 Cycle 1. In addition OS and CR will be explored in subgroups by geographical area (i.e. OS and CR analysis comparing treatments within each geographical area).

In each defined subgroup, the analysis will be carried out using the same type of methodology as described for the overall analysis of the corresponding endpoint. These results will be considered exploratory because of the multiplicity issue and also smaller sample sizes that cannot be pre-specified.

5.4 MULTIPLE COMPARISONS AND MULTIPLICITY

Secondary endpoints will be tested according to a fixed sequence method. If the primary endpoint is statistically significant, then the first secondary endpoint (according to the predefined list) will be tested, and so on for the other three secondary endpoints. When the sequence stops for a non-significant test the following tests will be downgraded to exploratory.

The secondary efficacy outcome measures for this study are ordered as follows:

- Morphologic CR rate
- Transfusion independence
- CR_{MRD}-rate
- CR_c rate

5.5 SIGNIFICANCE LEVEL

The overall significance level for the primary efficacy endpoint is 0.025 (one sided). As an interim analysis according to the O'Brien Fleming function for superiority and the Gamma family function (with $\gamma=-5.4695$ for non-binding futility) will be done after 260 events (2/3 of the total number of events), the respective significance levels are 0.00605 for the interim and 0.02314 for the final analysis. These significance levels will be re-computed at time of analysis based on the real fraction of information available.

Calculations of significance levels and related thresholds were performed by means of SAS PROC SEQDESIGN.

The following table shows probabilities to stop at interim analysis for futility or superiority with the null and alternative hypotheses for the primary endpoint:

Table 1 Probability to stop at Interim Analysis HA as Median OS	10 months	14 months
Gamma spending function $\gamma=-5.4695$ for futility	0.70094	0.01442
O'Brien Fleming for superiority	0.00605	0.58059

The following table shows probabilities of significant results for the first secondary endpoint, according to the chosen hierarchical procedure and assuming no need to consider the correction for multiplicity as 100% of information would be collected (which was the assumption at time of SAP V1). The reference alternative hypothesis is that the difference between treatments in the CR rate is 0.13 (having 0.20 as the rate for the placebo group). Probabilities are corrected by unconditional probability of significant results for the primary endpoint as conditional probability assumes the correlation between endpoints to be known. The obtained results are conservative and represent the lower probability bound assuming no correlation.

Table 2		
Secondary endpoint(s)		
Assumption: 100% information for secondary endpoint at interim analysis is available		
probability of significant results	0.13 rate difference	
	Independent from primary endpoint (i.e. as it was the only endpoint in the study)	Hierarchical procedure *
at Interim Analysis	0.91	0.55
Overall	0.91	0.82

* rounded power for the primary endpoint is 0.90 overall and 0.60 at interim analysis, respectively (median OS = 14 months vs. 10 months)

However, it is now assumed that not all the patients could be recruited at time of interim look or some of them could not be followed-up for enough time and considering that correlation between the primary endpoint and the secondary endpoints cannot be assumed to be null even if difficult to quantify (no correlation would have justified not correcting for multiplicity), a procedure that manages the multiplicity due to having planned for an interim analysis is needed. The Bonferroni correction (with 0.002 and 0.023 as the partition of the overall alpha level) will be adopted, regardless of the quantity of patients and the time of follow-up. Interpretation of p-values will be based on the hierarchy defined in section 5.4. The family-wise error rate of 0.025 will be adhered to [2, 3].

According to current recruitment rate, 85% of patients on average will have been recruited before the interim analysis time.

The O'Brien Fleming bound for the primary endpoint and Bonferroni criterium for the secondary endpoint(s) will then be adopted, leading to the probability of significant results being as reported in the following table.

Table 3		
Secondary endpoint(s) - probability of significant results at Interim/Final Analysis		
Assumptions: 85% of patients randomized and Bonferroni (0.002, 0.023)		
	0.13 rate difference	
	Independent from primary endpoint (i.e. as it was the only endpoint in the study)	Overall Hierarchical procedure **
Probability of significant results at Interim Analysis	0.56	0.34
Probability of significant results Overall	0.82*	0.74

power for the primary endpoint is rounded to 0.90 overall and 0.60 at interim analysis (median OS = 14 months vs. 10 months)

*assuming 0.6 as the probability to obtain significance at FA given failure at IA (as not all the 85% of patients will have been followed-up for more than 6 months)

** performing test on secondary endpoint also at FA in the case the primary is significant at IA but secondary is not

5.6 STATISTICAL NOTATION AND METHODOLOGY

Summary statistics for continuous variables will include the mean, standard deviation, minimum, first quartile (Q1), median, third quartile (Q3), and maximum. Categorical

variables will be presented as frequency counts and percentages, and time-to-event variables will be summarized using Kaplan-Meier estimates including median with 95% CI, number of events, number censored.

In general, frequency tables will be presented by treatment group and overall except for efficacy analysis or otherwise specified.

Data listings will be created to support each table and to present all data.

Means, LS means, medians, and quartiles will be rounded to 1 decimal place greater than the precision of the original value, while standard deviations and SEs will be rounded to 2 decimal places greater than the precision of the original value. Percentages for summarizing categorical data will be rounded to one decimal place.

P-values will be presented with 4 decimal places and values less than 0.0001 will be presented as < 0.0001 .

Unless otherwise noted, all data collected during the study will be included in data listings and will be sorted by treatment group, patient number and then by visit or event as relevant. Additional details and sorting order for each listing are presented in section 14.

In case at least one parameter in a table has missing values, a row/column with the number of missing values will be added. In case no missing values are documented at all for a table, no missing rows/columns will be presented, even if missing rows/columns are foreseen in the respective table shell.

In case more than one unscheduled visits fall in the same visit window (screening/cycle) without a value at the scheduled visit, the latest value will be included in summary tables based on cycle.

The final decision whether the PP set is relevant to the study and if tables of baseline characteristics need to be produced for the PP set, will be made at the BDRM.

5.7 DOCUMENTATION OF CLINICAL RESPONSE

Normally laboratory data needed for the assessment of clinical response are obtained from the central laboratory. In some cases, it is possible that data on peripheral blasts, neutrophil and platelet count needed for the assessment of response, are obtained from the site local laboratory when the central assessment is missing for any reason. These data will be collected in a specific form and separately listed only aimed to document response.

6 DATA HANDLING METHODS

6.1 MISSING DATA

6.1.1 Date Values

In cases of incomplete dates, the missing component(s) will be assumed as the most conservative value(s) possible.

Actual data values as they appear in the original CRFs will be shown in the data listings.

For the following dates specific imputation rules are defined:

Imputation of time to event variable dates:

Missing dates for time to event variables have to be avoided as far as possible.

The difference between the start date and the event date is calculated as time to event for the main efficacy variable and for some of the secondary variables.

Therefore the imputation of partial or complete missing event dates has to be handled using the most conservative approach. It is especially necessary to distinguish between active treatment and placebo group in this respect. As events analysed in this study are “negative” events, the following rules can be considered as conservative.

Imputation rules for missing event date

for patients who received active treatment (Pracinostat):

- If “day” is the only missing field, impute the “day” as the first day of the month documented or the last visit date within the documented month, where the absence of the event is documented.
- If “day” and “month” are missing, impute the “day” and “month” as 01 January of the year documented or the last visit date within the documented year, where the absence of the event is documented.
- If “day”, “month”, and “year” are all missing, the date of event is imputed as the date of the last visit date where the absence of the event is documented.

for patients who received Placebo:

- If “day” is the only missing field, impute the “day” as the last day of the month documented or the last visit date within the documented month, where the absence of the event is documented.
- If “day” and “month” are missing, impute the “day” and “month” as 31 December of the year documented or the last date within the documented year where the absence of the event is documented.
- If “day”, “month”, and “year” are all missing, the date of event is imputed as the date of the last visit documented where the absence of the event is documented.

For missing start dates of duration of response, rules for placebo should be used for pracinostat and viceversa, to be conservative.

Imputation of time of new AML therapies:

Missing dates for new AML therapies (either those started after study treatment stop or concomitant to study treatment stop) have to be avoided as far as possible.

The imputation of partial or complete missing start and end dates of new AML therapies have to be handled using the most conservative approach. It is especially necessary to distinguish between active treatment and placebo group in this respect. As events analysed in this study are “negative” events, the following rules can be considered as conservative.

General rules for imputation are:

- any imputed date should be before the date of death or the last day the patient was alive
- the end date of the therapy should be greater or equal to the start date of the therapy

If more than one new AML therapy is given to a patient during study period only the first start date of the new therapies is relevant for the censoring processes (selection of the first start date will be done after any imputations).

Imputation rules for missing **start date** of the first new AML therapy

for patients who received **active treatment** (Pracinostat):

- If “day” is the only missing field, impute the “day” as the first day of the month documented. If month and year are equal to the start of the study treatment impute the date as the first treatment day.
- If “day” and “month” are missing, impute the “day” and “month” as 01 January of the year documented or the start of the study treatment if the year is the same as for treatment start.
- If “day”, “month”, and “year” are all missing, the date of the start of the new AML therapy is imputed as the date of the start of the study treatment.

for patients who received **Placebo**:

- If “day” is the only missing field, impute the “day” as the last day of the month documented.
- If “day” and “month” are missing, impute the “day” and “month” as 31 December of the year documented or as 01 January if the year is the same as for treatment start.
- If “day”, “month”, and “year” are all missing, the date of event is imputed as 01 January of the year when the study treatment started.

Imputation rules for missing **end date** of the first new AML therapy

for patients who received **active treatment** (Pracinostat):

-
- If “day” is the only missing field, impute the “day” as the last day of the month documented.
 - If “day” and “month” are missing, impute the “day” and “month” as 31 December of the year documented.
 - If “day”, “month”, and “year” are all missing or if “ongoing” is documented, the date is imputed as the last date known alive .

for patients who received **Placebo**:

- If “day” is the only missing field, impute the “day” as the first day of the month documented.
- If “day” and “month” are missing, impute the “day” and “month” as 01 January of the year. If the year documented is equal to the year of the start of the study treatment, the date of the end of the new AML treatment is imputed as the start date of the new AML treatment.
- If “day”, “month”, and “year” are all missing or “ongoing” is documented, the date is imputed as the last date known alive.

Imputation of Adverse Event dates:

Missing AE dates will be queried as far as possible taking other information (eg, relatedness to study drug, first intake of study drug) into account.

For missing AE start or end date, imputation rules follow the principle that the AE is regarded as treatment-emergent AE (TEAE) when a connection to the start and end of the treatment period could not be excluded (by the documented partial dates or other relevant information in the CRF).

Imputations of adverse events are used for slotting events to the appropriate study time periods and for sorting in data listings. They will not be used to calculate duration of AEs. If an AE start or end date is missing, then the duration of the AE will be set to missing.

Remaining missing dates will be imputed as follows:

For AE start date, imputation rule is to conservatively capture AEs with missing start dates as treatment-emergent AEs (TEAEs):

- If “day” is the only missing field, impute the “day” as the first dose date if their “month” are the same. Otherwise impute the “day” as the first day of the month documented.
- If “day” and “month” are the only missing fields, impute the “day” and “month” as the first dose date if their “year” is the same. Otherwise impute the “day” and “month” as the first of January of the year documented.
- If “day”, “month”, and “year” are all missing, to be conservative, the AE will be assumed to occur on the same day as the first dose was administered.

For AE end date, imputation rule is to conservatively capture AEs with missing end dates as treatment-emergent AEs (TEAEs):

- If “day” is the only missing field, impute the “day” as the last day of the month documented if their “month” are the same.
- If “day” and “month” are the only missing fields, impute the “day” and “month” as December 31 of the year, if the patient is alive at that date. Otherwise impute the date of death.
- If “day”, “month”, and “year” are all missing, to be conservative, the AE will be assumed to be ongoing at the end of the study for the respective patient.

Imputation of Concomitant Medication dates

Impute start and end dates for use to derive the reference variables for concomitant medication start and end relative to treatment. The reference variables will be used to differentiate before, during and after treatment for the concomitant medication.

For concomitant medication start date, imputation rules are as follows:

- If “day” is the only missing field, impute the “day” as the first dose date if their “month” are the same and the reference variable will be set to “during treatment”. Otherwise impute the “day” as the first day of the month documented.
- If “day” and “month” are the only missing fields, impute the “day” and “month” as the first dose date if their “year” is the same and the reference variable will be set to “during treatment”. Otherwise impute the “day” and “month” as the first of January of the year documented.
- If “day”, “month”, and “year” are all missing, do not impute completely missing concomitant medication start dates; all values that depend on this date will be set to missing. The reference variable will be set to “during treatment”.

For concomitant medication end date, provided that imputed date cannot be prior to start date, imputation rules are as follows:

- If “day” is the only missing field, impute the “day” as the earliest of the last day of the month documented and the last safety assessment visit date in the documented month. The reference variable will be set to “during treatment” if the imputed date is not before first randomized study medication.
- If “day” and “month” are the only missing fields, impute the “day” and “month” as the earliest of December 31 and the last safety assessment visit date in the documented year. The reference variable will be set to “during treatment” if the imputed date is not before first randomized study medication.
- If “day”, “month”, and “year” are all missing, do not impute completely missing concomitant medication end dates; all values that depend on this date will be set to missing. The reference variable will be set to “during treatment” if the imputed date is not before first randomized study medication.

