3.3 SAMPLE SIZE CONSIDERATIONS

This is an event-driven study. Sample size was computed for a group-sequential design with stopping rules for both futility and superiority (study-wise one-sided alpha level=0.025, power 0.90) with one interim analysis at 67% (2/3) of information and a final analysis. The alpha error spending function is from the O'Brien Fleming function for superiority and the Gamma family (with $\gamma=-5.4695$, more conservative than O'Brien Fleming) for futility (non-binding). Proportionality of hazards is assumed. Assuming that median OS is 10.0 months in the Group B (placebo + AZA) the aim is to detect, by means of the log-rank test or equivalent, an increase to 14.0 months in Group A (pracinostat + AZA), i.e. a HR of 0.714286. A total of 390 events (deaths) allows to meet a power requirement of at least 90% (actually 90.87%; it was 90% with the original function used in v1 protocol; further calculations kept fixed the number of events needed) at a study-wise one-sided significance level of 0.025.

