8.1 PRIMARY EFFICACY ANALYSIS

The primary efficacy endpoint is overall survival (OS) measured as the time from randomization until death from any cause. The primary set of analysis will be the ITT set.

OS time for patients alive at their last assessment of survival status will be right censored

- At the documented date of the last assessment during follow-up (which should finally correspond to the date reported in the end of long-term follow-up) in the CRF, in the case that the long-term follow-up is filled in,
- At the last assessment of survival status available in the case that the long-term follow-up is not filled in.

OS will not be censored at the time of subsequent interceding therapies, if the patient received any. Final analysis will take place after the required number of events (390 deaths) has occurred or after the decision to stop the trial because of futility or superiority at time of the interim analysis.

Missing start or end dates for the calculation of OS will be imputed as described in section [6.1.1](#).

The primary OS analysis will be based on the log-rank test stratified by ECOG PS and cytogenetic risk (both ECOG PS and cytogenetic risk values used for the randomization) comparing the two survival functions of the active treatment group and placebo at the overall one-sided alpha = 0.025 level of significance (a group sequential design according to Gamma family spending function, adopting $\gamma=-3.6$ (similar to O'Brien Fleming) for superiority and $\gamma=-5.5$ (more conservative than O'Brien Fleming) for futility (non-binding)) is used).

Additionally, the duration of the follow-up will be calculated using a reverse KM analysis, considering an event in patients who are alive and censoring patients at their date of death.

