Time to CR is defined as the time from the date of randomization until the date of first CR in the absence of interceding therapies.

The analysis set will be the ITT set.

Time to CR will be censored at the date of the last assessment of patient status excluding CR in the case no CR occurred by time of analysis. In case of interceding therapies, PD or death, time to CR will be censored to the start date of the interceding therapy, PD assessment date or death date respectively. Cumulative Incidence Function (CIF) will be computed as 1-Kaplan Meier curve and treatment groups will be compared by the stratified (cytogenetic risk and ECOG PS at randomization) log-rank test.

Morphologic Complete Remission (CR) within 6 cycles rate

Morphologic complete remission (CR) within the first 6 cycles rate is defined as the proportion of patients who achieve CR in the absence of interceding therapies within 6 treatment cycles (i.e. during treatment phase up to Day 1 of Cycle 7 included). Analysis will be performed in the ITT set.

CR within 6 cycles rate will be analyzed using the same methods as those used for the CR rate analysis, limited to the stratified analysis. Patients for whom no efficacy assessment is available will be analyzed as not having CR.

Best Response

A summary table including the best response obtained during study course will also be presented (number of patients and related percentage).

For each patient the response assessment will be classified as best response using the following criteria:

- Morphologic Complete Remission (CR) as highest level,
 - Cytogenetic Complete Remission (CRc)

followed by

- Morphologic complete remission with incomplete blood count recovery (CRi),
- Morphologic leukemia free state (MLFS)
- Partial Remission (PR),
- Stable disease (SD)
- Progression

and the two summary response classifications:

- Composite Complete Response (patients with at least MLFS)
- Overall Response (patients with CR or CRi or MLFS or PR)

The criteria used for the single responses will be adequately used also for the two summary classifications.

The analysis sets will be the ITT and the EE-1 set. The corresponding ITT-2 and EE-2 sets will be the basis for the analysis of CRc.

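### Partial event dates are imputed early for pracinostat and late for placebo, which biases the primary OS comparison against pracinostat and, for the exploratory Time to CR, works in its favour

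*SAP*

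**What the plan says.** SAP 6.1.1 covers dates of time-to-event variables and sets the principle: "Therefore the imputation of partial or complete missing event dates has to be handled using the most conservative approach". It separates active from placebo patients on the ground that the events analysed are unfavourable.

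| Missing part | Received pracinostat | Received placebo |
|---|---|---|
| Day | First of the month, or last event-free visit in that month | Last of the month, or last event-free visit in that month |
| Day and month | 1 January, or last event-free visit in that year | 31 December, or last event-free date in that year |
| Whole date | Last event-free visit | Last event-free visit |

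The placebo wording for a missing day is "as the last day of the month documented or the last visit date within the documented month"; the text does not say when each alternative applies. The direction is swapped in one case only, the start date of duration of response.

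SAP 8.1 brings this into the primary analysis: "Missing start or end dates for the calculation of OS will be imputed as described in section" 6.1.1. SAP 8.3 adds an endpoint whose event is favourable: "Time to CR is defined as the time from the date of randomization until the date of first CR". The table of planned efficacy analyses (SAP 13) lists no OS analysis under a common date rule. SAP 8.1.2 leaves other OS sensitivity analyses to be decided before unblinding, for example at the blind data review meeting.

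**The concern.** Two patients with the same partial death date get different OS times according to treatment. That is a systematic shift, not noise, and it sits in the primary analysis rather than in a sensitivity analysis. For OS it moves the hazard ratio upward and costs power.

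There are three further defects:

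- **Time to CR.** An early event date helps here. The same rule dates pracinostat remissions early and placebo remissions late, which favours pracinostat. Because start dates of duration of response are swapped, one partial CR date takes opposite values in Time to CR and duration of CR.
- **Last-visit alternative.** As a lower bound it makes sense for pracinostat. For placebo a lower bound never binds, because no visit in a month falls after its last day. Read literally as an alternative, it gives placebo an early date, against the rule's intent.
- **Coverage.** The rule is keyed to treatment received, whereas ITT includes randomized patients who were never dosed (SAP 4.1), so they have no rule. No cap at the data cut-off is stated, so 31 December could fall after it.

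**Working it through.** **1. Inputs from the documents.** SAP 3.3: "study-wise one-sided alpha level=0.025, power 0.90"; "Assuming that median OS is 10.0 months in the Group B (placebo + AZA"), against 14.0 months, "i.e. a HR of 0.714286"; and "A total of 390 events (deaths) allows to meet a power requirement of at least 90% (actually 90.87"%). SAP 5.5: one-sided levels 0.00605 (260 deaths) and 0.02314 (390 deaths). SAP 8.1.1: futility p 0.29906. Protocol 9.11: 500 patients, 100 in year 1 and the rest over the next 1.5 years.

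**2. Reproducing the plan's figures.** Drift = |ln HR| × √D / 2 = 0.33647 × √390 / 2 = 3.322 at the final analysis and 0.33647 × √260 / 2 = 2.713 at the interim. O'Brien-Fleming-type spending at 2/3 information gives 0.00605 (z = 2.509) and 0.02314 (z = 1.993). Bivariate normal integration with the futility bound observed gives power 0.9087, as stated. The HR bounds exp(−2z/√D) are 0.7325, 0.9367 and 0.8172, which match SAP 8.1.1 and 8.1.2. A single look at 0.02314 has power Φ(3.322 − 1.993) = 0.908, the benchmark for the simulation.

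**3. Size of the date shift.** For dates spread evenly over the period, the gap between arms is the period length less one day.

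- Day missing: 30.44 − 1 ≈ 29.4 days (about 14.7 early on pracinostat, 14.7 late on placebo).
- Day and month missing: 365.25 − 1 ≈ 364 days (about 182 each way).

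**4. Effect on OS, true HR 0.714.** Monte Carlo: 6,000 trials per scenario, cut at the 390th death, unstratified log-rank, single look at 0.02314. The shares of partial death dates are **assumptions**.

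| Deaths with partial date | Mean HR | Mean z | Success |
|---|---|---|---|
| None | 0.712 | 3.312 | 90.6% |
| 5% day only | 0.714 | 3.283 | 90.0% |
| 10% day only | 0.716 | 3.255 | 89.6% |
| 20% day only | 0.720 | 3.198 | 88.5% |
| 2% day and month | 0.722 | 3.182 | 88.3% |
| 5% day and month | 0.736 | 2.990 | 84.2% |
| 5% day and month, pracinostat not before last visit | 0.727 | 3.109 | 86.6% |
| 10% day and month | 0.761 | 2.676 | 75.4% |

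Cross-check with Φ(mean z − 1.993): for 5% day and month, Φ(0.997) = 0.841; with the last-visit floor, Φ(1.116) = 0.868. Both agree with the simulation. Loss at 5% day and month: 90.6 − 84.2 = 6.4 points, or 90.6 − 86.6 = 4.0 with the floor. Monte Carlo error is about 0.4 points, with rules compared on the same simulated data.

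**5. Effect on OS, true HR 1.** Rejection is 2.1% with no missing dates, 1.6% with 10% day-only (mean HR 1.010) and 0.9% with 5% day and month (mean HR 1.040). Under a common mid-period rule the mean HR is 1.003. The error rate falls; it does not rise.

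**6. Time to CR, equal arms.** 3,000 trials with assumed CR timing and censoring. One-sided false positives for pracinostat: 2.5% with complete dates, 2.9% with 10% day-only, and 3.1% and 4.0% with 5% and 10% lacking day and month. In the last two, CR appears 13.5 and 27 days earlier on pracinostat. Monte Carlo error is about 0.3 points, so only the direction is firm at the low end.

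**7. One mid-month or mid-year rule for both arms.** OS success is 90.5 to 90.6% in every scenario, rejection under HR 1 is 2.1 to 2.2%, and Time to CR false positives are about 2.5%.

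**The case against.** The rule is pre-specified, works against the sponsor's own drug on the primary endpoint and cannot create a false superiority claim. Partial death dates should also be few. SAP 6.1.1 asks that they be avoided, survival contact is every 3 months (protocol 5.2), and the event set is validated before analysis (protocol 9.12). A death with a known year but unknown month should be rare. All of this stands, and it limits the size of the problem.

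Time to CR is exploratory, and marrow sampling is scheduled, so partial CR dates should be scarce. SAP 6.1.1 does not name Time to CR, so applying the rule to it is a reading of the text. The section does cover time-to-event variables in general and makes no exception for Time to CR. If the endpoint is outside the rule, it has no rule.

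A reader might infer more than the documents support:

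- *OS data sets cannot be dry-run blind.* Dummy codes suffice, SAP 11 records a dry run before the interim, and SAP 8.1.1 gives the interim analysis to an unblinded statistician. Only the final dates need the real codes.
- *A large power loss is to be expected.* The larger losses need an assumed 2 to 5% of deaths with no month, and they shrink if pracinostat dates are floored at the last visit.
- *The trial could be stopped wrongly for futility.* The shift is toward that bound, but futility is non-binding and SAP version 5 was written after the interim results were unblinded.
- *The change costs only wording.* At that stage, replacing the primary rule moves the HR in pracinostat's favour.

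**Conclusion.** The point holds as a modest one. The primary OS comparison is biased against pracinostat by construction, without inflation of type I error. Fully missing dates are unaffected, since both arms follow the same rule. The loss of power is about 0.5 to 1 point if 5 to 10% of deaths lack only the day, about 2 points if 2% lack day and month, and 4 to 6 points if 5% do (the lower figure with the last-visit floor). These sizes rest on assumed shares of partial dates, exponential survival, and an unstratified single-look test.

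Two defects do not depend on any share. The last-visit alternative is ambiguous and, taken literally, defeats the rule for placebo. The stated rationale does not hold for Time to CR, where the rule favours pracinostat and conflicts with the date used for duration of CR.

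**What to change.** Use one arm-independent rule for event dates in OS, PFS, RFS, the durations and Time to CR: mid-month if the day is missing, mid-year if day and month are missing, never before the last date the event was known absent and never after the data cut-off. Keep the arm-specific rule only as a labelled worst-case OS sensitivity analysis.

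The cost is SAP wording, one programming rule, and a main OS analysis that is no longer worst-case against pracinostat. Because SAP version 5 followed interim unblinding (SAP 11), a change made then needs a written justification that does not rest on the observed results.

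If the primary rule is kept for that reason:

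1. Add the common-rule OS analysis to SAP 13 as a pre-specified sensitivity analysis.
2. State that the last-visit date is a lower bound only.
3. Remove Time to CR from the arm-specific rule.

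Either way, report the number of partial death dates by arm and by missing component.
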